2. STUDY INFORMATION, OBJECTIVES, AND ENDPOINTS

2.1. Protocol and Case Report Form Version

This SAP is based on INCB 50465-206 Protocol Amendment (Version) 5 dated 02 NOV 2020 and CRFs approved 04 JUN 2020. Unless superseded by an amendment, this SAP will be effective for all subsequent Protocol Amendments and CRF versions.

2.2. Objectives and Endpoints

Objectives	Endpoints
Primary	

• To evaluate the efficacy of INCB050465 in the treatment of participants with AIHA.	
• Proportion of participants attaining a CR (defined as hemoglobin ≥ 12 g/dL not attributed to transfusion effect*) at any visit from Week 6 to Week 12.• Proportion of participants attaining a PR (defined as hemoglobin 10-12 g/dL or at least ≥ 2 g/dL increase from baseline not attributed to transfusion effect) at any visit from Week 6 to Week 12. 
*No transfusion effect definition: > 1 week since last transfusion.

• To evaluate the safety of INCB050465 administered as repeat doses in participants with AIHA.	
• Safety and tolerability will be assessed by monitoring AEs, measuring vital signs and ECGs, and conducting clinical laboratory blood and urine sample assessments.
Secondary	

• To further evaluate the efficacy of INCB050465 in the treatment of participants with AIHA.	
• Proportion of participants attaining a CR during postbaseline visits.• Proportion of participants attaining a PR during postbaseline visits.• Proportion of participants attaining a ≥ 2 g/dL increase in hemoglobin from baseline.• Mean, change, and percentage change from baseline of hemoglobin.• Proportion of participants requiring transfusions.• Proportion of participants who achieve normalization of hemolytic markers. (Hemolysis markers: hemoglobin, haptoglobin, LDH, reticulocyte count, total bilirubin, and direct/indirect bilirubin.)• Change of daily usage of prednisone.• FACIT-F subscale assessment.

• To evaluate the PK effects of INCB050465.	
• PK endpoints: C_{\max}, t_{\max}, C_{\min}, AUC_{0-t}, and CL/F.

Objectives	Endpoints

• To evaluate the PD effects of INCB050465.	
• Change from baseline in PD markers: reticulocyte count, DAT for IgG and C3b, cold agglutinin levels, haptoglobin, total bilirubin, direct/indirect bilirubin, LDH, and complement assessment (CH50, C3, and C4).

3. STUDY DESIGN

This is a multicenter, open-label study designed to evaluate the safety and efficacy of INCB050465 administered orally to participants with AIHA who have decreased hemoglobin and evidence of ongoing hemolysis that requires treatment intervention. Participants with primary warm, cold (CAD), and mixed-type AIHA, without an underlying lymphoproliferative malignancy or other autoimmune disease and have failed at least 1 prior treatment for AIHA will be eligible for enrollment. Participants will be treated for 12 weeks. There are 2 cohorts in this study: Cohort 1, with up to 10 participants, with no more than 3 cold (CAD)/mixed-type AIHA participants to appropriately reflect response in the overall population, which is predominantly warm AIHA; and Cohort 2, with approximately 15 participants, with approximately 5 CAD AIHA, up to 8 warm AIHA, and the remainder from any of the 3 AIHA types. Cohort 2 distribution and increased number of participants are intended to better evaluate CAD AIHA patients and possible signal observed in Cohort 1, as well as account for higher baseline variability seen in the warm AIHA subpopulation. The first cohort (Cohort 1, n = 10 participants) enrolled will initially receive INCB050465 1 mg QD. At Week 6, participants who continue to require transfusions or do not attain a meaningful clinical response (at least a stabilization \geq 2 g/dL increase in hemoglobin from baseline to Week 6) may have their dose increased, with sponsor preapproval, to 2.5 mg QD of INCB050465 until Week 12. If there are any tolerability issues in individual participants who received 2.5 mg, the dose may be decreased to 1 mg. Following enrollment of a minimum of 6 warm AIHA participants in the first cohort and review of safety and efficacy data through Week 6, Cohort 2 may begin enrollment. Participants in Cohort 2 (n \approx 15) will receive INCB050465 2.5 mg QD for 12 weeks. If there are any tolerability issues, the dose may be decreased to 1 mg. The investigator and sponsor should review and agree any dose increases or decreases. Following the last dose of INCB050465, participants will be eligible for a 12-week (3 months) follow-up for evaluation of the safety and durability of response.

3.1. Randomization

Not applicable.

3.2. Control of Type I Error

All statistical analyses are exploratory in nature. No alpha control will be implemented. Unless otherwise specified, all confidence intervals provided will be at the 95% confidence level.

3.3. Sample Size Considerations

The sample size is based on the precedent of other studies and is not based on statistical power calculations ([Go et al 2017](#), [Hill et al 2017](#), [Lechner and Jäger 2010](#)). The study is not powered for statistical comparison of efficacy endpoints; the sample size is based on the demonstration of preliminary findings of clinical response. It is anticipated that a sample size of approximately 25 participants will permit sufficient data to warrant further investigation. Also, the sample size depends on the occurrence of safety findings. Approximately 10 participants will be enrolled in Cohort 1, and approximately 15 participants in Cohort 2, which will provide > 89% chance of detecting at least 1 AE of interest (eg, colitis, exfoliative dermatitis, infections) if the underlying AE rate is 20% for Cohort 1 and > 96% chance for Cohort 2.

3.4. Schedule of Assessments

Refer to Protocol Amendment (Version) 5 dated 02 NOV 2020 for a full description of all study procedures and assessment schedules for this study.

4. DATA HANDLING DEFINITIONS AND CONVENTIONS

4.1. Scheduled Study Evaluations

4.1.1. Day 1

Day 1 is the date that the first dose of study drug INCB050465 is administered to the participants.

4.1.2. Study Day

If a visit/reporting date is on or after Day 1, then the study day at the visit/reporting date will be calculated as

$$\text{Day \#} = (\text{Visit/Reporting Date} - \text{Day 1 date} + 1).$$

If the visit/reporting date is before Day 1, then the study day at the visit/reporting date will be calculated as

$$\text{Day \#} = (\text{Visit/Reporting Date} - \text{Day 1 date}).$$

A study day of -1 indicates 1 day before Day 1.

4.1.3. Baseline Value

Baseline is the last nonmissing measurement obtained before the first administration of INCB050465.

When scheduled assessments and unscheduled assessments occur on the same day and time of the assessment or time of first dose is not available, use the following convention to determine baseline:

- If both a scheduled and an unscheduled visit are available on the day of the first dose and the time is missing, use the scheduled assessment as baseline.
- If all scheduled assessments are missing on the day of the first dose and an unscheduled assessment is available, use the unscheduled assessment as baseline.

4.1.4. Handling of Missing and Incomplete Data

In general, values for missing data will not be imputed unless methods for handling missing data are specified in relevant sections.

4.2. Variable Definitions

4.2.1. Body Mass Index

Body mass index will be calculated as follows:

$$\text{BMI (kg/m}^2\text{)} = [\text{weight (kg)}] / [\text{height (m)}]^2.$$

4.2.2. Prior and Concomitant Medication

Prior medication is defined as any nonstudy medication started before the first dose of INCB050465.

Concomitant medication is defined as any nonstudy medication that is:

- Started before the date of first administration of INCB050465 and is ongoing throughout the study or ends on/after the date of first administration of INCB050465.
- Started on/after the date of first administration of INCB050465 and is ongoing or ends during the course of study treatment.

A prior medication could also be classified as "both prior and concomitant medication" if the end date is on or after first administration of INCB050465. In the listing, it will be indicated whether a medication is prior-only, concomitant-only, or both prior and concomitant.

For the purposes of analysis, all medications will be considered concomitant medications unless the medications can unequivocally be defined as not concomitant.

5. STATISTICAL METHODOLOGY

5.1. General Methodology

Unless otherwise noted, SAS® software (SAS Institute Inc, Cary, NC; Version 9.1 or later) will be used for the generation of all tables, graphs, and statistical analyses. Descriptive summaries for continuous variables will include, but not be limited to, the number of observations, mean, standard deviation, median, minimum, and maximum, and both the actual value and change and/or percentage from baseline (if available) will be analyzed. Descriptive summaries for categorical variables will include the number and percentage of participants in each category. All by-visit analyses will include the follow-up period if the data are available.

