1. PROTOCOL SUMMARY

Protocol Title: A Phase 2, Open-Label Study of INCB050465 in Participants With

Autoimmune Hemolytic Anemia

Protocol Number: INCB 50465-206

Objectives and Endpoints:

Objectives	Endpoints
Primary	
To evaluate the efficacy of INCB050465 in the treatment of participants with AIHA.	• Proportion of participants attaining a CR (defined as hemoglobin > 12 g/dL not attributed to transfusion effect* and the normalization of hemolytic markers) at any visit from Week 6 to Week 12.
	• Proportion of participants attaining a PR (defined as hemoglobin 10-12 g/dL or ≥ 2 g/dL increase from baseline not attributed to transfusion effect and the normalization of hemolytic markers) at any visit from Week 6 to Week 12.
	*No transfusion effect definition: >1 week since last transfusion.
To evaluate the safety of INCB050465 administered as repeat doses in participants with AIHA.	Safety and tolerability will be assessed by monitoring AEs, measuring vital signs and ECGs, and conducting clinical laboratory blood and urine sample assessments.

Overall Design:

Study Phase	Phase 2
Clinical Indication	AIHA
Population	Men and women, aged 18 years or older with primary AIHA without evidence of a lymphoproliferative malignancy.
Number of Participants	Approximately 25
Study Design	Open-label, multicenter study
Estimated Duration of Study	Treatment duration will vary among participants. The initial study period will be 28 weeks in duration. For participants who are eligible for an extension of treatment based on their clinical response, the treatment duration may be extended with sponsor approval.
Safety Review Committee	Yes (internal)

Treatment Groups and Duration:

Participation is 28 weeks for participants who are not eligible for an extension based on clinical response and includes the following:

• Screening: up to 28 days

• Treatment: up to 12 weeks

- Extension period: For participants receiving benefit from study drug, further participation may continue with sponsor approval until the drug is available through another clinical study, or is commercially available, or the sponsor stops the study or the study drug development.
- Follow-up: up to 12 weeks (3 months)

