Table 1: Schedule of Assessments

		Screening				Trea	tment					Follow-Up ^a	ı
Procedure	Protocol Section		Day 1	Wk 1 ± 3 days	Wk 2 ± 3 days	Wk 4 ± 3 days	Wk 6 ^b ± 3 days	Wk 8 ± 3 days	Wk 10 ± 3 days	Wk 12 ± 3 days (EOT)	Month 1 + 5 days	Month 2 ± 5 days	Month 3 ± 5 days (EOS)
Administrative procedures													
Informed consent	8.1.1	X											
Contact IRT	8.1.3	X	X	X	X	X	X	X	X	X	X	X	X
Review inclusion and exclusion criteria	5.1, 5.2	X	X										
Demography and medical history	8.1.4	X											
Prior/concomitant medications	8.1.5	X	X	X	X	X	X	X	X	X	X	X	X
Study drug accountability and assess compliance	6.5			X	X	X	X	X	X	X			
Study drug dispensing	6.1		X			X		X					
Prophylactic treatment for PJP	6.7.1.1		X	X	X	X	X	X	X	X	X	X	X
Safety procedures/assessments													
Physical examination ^c	8.3.2	Xc	X ^{c,d}	X	X	X		X		X			Xc
Vital signs ^e	8.3.3	X	X	X	X	X	X	X	X	X			X
Serology ^f	8.3.5.7	X											
D-Dimer	8.3.5.5	X				X		X		X			
Vitamin B12/folic acid	8.3.5.2	X											
FSHg	8.3.5.6	X											
Serum pregnancyh	8.3.5.6	X											
Urine pregnancy ^h	8.3.5.6		X	X	X	X	X	X	X	X			
Urinalysis	8.3.5.4	X								X			
Serum chemistries ⁱ	8.3.5.1 8.3.5.3	X	X	X	X	X	X	X	X	X	X	X	X
12-Lead ECG ^j	8.3.4	X			X			X		X			
AE assessment	8.3.1	X	X	X	X	X	X	X	X	X	X	X	X

Table 1: Schedule of Assessments (Continued)

		Screening	Treatment							Follow-Up ^a			
Procedure	Protocol Section	Days -28 to -1	Day 1	Wk 1 ± 3 days	Wk 2 ± 3 days	Wk 4 ± 3 days	Wk 6 ^b ± 3 days	Wk 8 ± 3 days	Wk 10 ± 3 days	Wk 12 ± 3 days (EOT)	Month 1 + 5 days	Month 2 ± 5 days	Month 3 ± 5 days (EOS)
Efficacy assessments													
Hematology	8.2.1	X	X	X	X	X	X	X	X	X	X	X	X
Hemolysis markers ^k	8.2.1	X	X	X	X	X	X	X	X	X	Xk	X^k	Xk
DAT and cold agglutinin levels	8.2.2	X								X			
Complement assessment (CH50, C3, and C4)	8.2.1		X							X			
FACIT-Fatigue sub-scale	8.2.3		X				X			X	X	X	X
PK plasma sampling ^l	8.4			X	Xm			Xm		X			

^m No food intake 4 hours predose and 1 hour postdose on Weeks 2 and 8.

VV-CLIN-000602 CONFIDENTIAL

^a For participants who are not eligible to enter into the extension period.

^b Dose modification.

^c Comprehensive physical examination at screening, Day 1, and EOS; targeted physical examination at all other time points.

^d Height and body weight will only be assessed at Day 1.

^e Vital signs will include body temperature, respiratory rate, blood pressure, and pulse.

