f Serology includes HIV, hepatitis, anti-Streptolysin antibody, and anti-phospholipid antibody tests.

g For women of nonchildbearing potential only (ie, surgically sterile with a hysterectomy and/or bilateral oophorectomy OR postmenopausal, defined by last menstrual period > 12 months before screening and confirmed by FSH).

^h For women of childbearing potential only.

¹ Ferritin, iron, and total iron-binding capacity will be tested at screening for all participants and at Week 6 if the participant has ongoing transfusions requirements during the study.

Single ECG. At screening, in the event that a single QTcF is > 470 milliseconds for males or > 480 milliseconds for females, triplicate ECG measurements may be performed.

k Hemoglobin, haptoglobin, LDH, reticulocyte count, total bilirubin and direct/indirect bilirubin are hemolytic markers will be measured. During follow-up, these hemolytic markers should be assessed if a participant becomes symptomatic or starts new treatment; relevant biomarkers should also be included.

Plasma for PK analysis will be collected predose and 1, 2, and 4 hours postdose at Weeks 2 and 8. Predose PK will be collected at Weeks 1 and 12.

Table 2: Schedule of Assessments for the Extension Period

		Extension Period			Follow-Up	
Procedure	Protocol Section	At Least Every 8-12 Weeks in Clinic	EOT Extension Period	Month 1 + 5 days	Month 2 ± 5 days	Month 3 ± 5 days (EOS)
Prior/concomitant medications	8.1.5	X	X	X	X	X
Study drug dispensing	6.1	X				
Study drug accountability and assess compliance	6.5	X	X			
AE assessment	8.3.1	X	X	X	X	X
Prophylactic treatment for PJP	6.7.1.1	X	X	X	X	X
Hematology ^{a,b}	8.2.1	X	X	X	X	X
Hemolysis markers ^a	8.2.1	X	X	X	X	X
Serum chemistries ^a	8.3.5.1	X				

^a Performed at each site as per the standard of care for participant's condition and monitoring at the investigator's discretion. Frequency to be determined by the investigator if it is necessary to monitor any other ongoing clinical condition.

^b Hematology panel will be performed at local laboratory.

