An internal Safety Review Committee (see Section 9.6) will review clinical response and AE data. If there is no clinical response (CR or PR) by Week 12 in the first cohort of 10 participants, including those who receive dose escalation to 2.5 mg, the study will be stopped for futility. If there is a clear emerging signal from either Cohort 1 or Cohort 2, the committee may make recommendations as to the expanded study of either cohort to obtain additional safety and efficacy data at either dose level.

Participants who complete the 12-week treatment period and demonstrate clinical benefit from study drug may enter into an extension period with sponsor approval to continue receiving INCB050465 until the drug is available through another clinical study, or is commercially available, or the sponsor stops the study or the study drug development. Visits during the extension period will be conducted every 8 to 12 weeks to continue to monitor the effectiveness of the clinical response, as well as clinical safety laboratory assessments and adverse events.

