7. DISCONTINUATION OF STUDY TREATMENT AND PARTICIPANT DISCONTINUATION/WITHDRAWAL

7.1. Discontinuation of Study Treatment

The decision to discontinue study drug will not constitute study completion. In the event that study drug is discontinued, the treatment period will be considered complete, and the follow-up period will begin.

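### Do the follow-up rows of the by-visit efficacy tables need a rule on visits, denominators and extension participants?

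*SAP*

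**What the plan says.** SAP 5.1 sets the general rule: "All by-visit analyses will include the follow-up period if the data are available". It asks for the number of observations in continuous summaries, and for number and percentage in categorical ones, without naming the base. SAP 4.1.4 imputes nothing unless a section says otherwise. SAP 5.3.1 assigns all efficacy analysis to the FAS.

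The protocol has two sets of follow-up visits at Months 1, 2 and 3.

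- **Table 1**, after Week 12. Its footnote a restricts these visits: "For participants who are not eligible to enter into the extension period". The summary in Section 1 agrees: "Participation is 28 weeks for participants who are not eligible for an extension based on clinical response".
- **Table 2**, after the end of extension dosing, with the same month labels.

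Protocol 4.1 describes entry to the extension ("Participants who complete the 12-week treatment period and demonstrate clinical benefit from study drug may enter into an extension period with sponsor approval") and the purpose of its visits ("Visits during the extension period will be conducted every 8 to 12 weeks to continue to monitor the effectiveness of the clinical response"). Protocol 7.1 covers early stoppers: "In the event that study drug is discontinued, the treatment period will be considered complete, and the follow-up period will begin".

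In SAP Appendix A, the ten efficacy tables (2.1.1 to 2.2.8) are listed for the FAS only. Tables numbered with a final X, all of them safety or exposure tables, also get an extension-period version.

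**The concern.** The rule in SAP 5.1 can be read in two ways.

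1. **Only Table 1 follow-up enters.** Participants with benefit tend to leave the rows after Week 12, so a response rate could fall although nobody lost a response.
2. **Table 2 follow-up is pooled in.** One month label then mixes follow-up after 12 weeks of dosing with follow-up after open-ended dosing.

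In either case the percentage depends on whether the base is the FAS or those assessed. Protocol 4.1 and SAP 3 give durability of response as one purpose of follow-up. SAP 10.1 says the interim is to support publications and a possible Phase 3 plan in CAD. A reader who took a falling follow-up row for relapse, or a stable one for durability, could be misled. The lack of any extension version of an efficacy table seems to leave response in the extension without a display.

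**Working it through.** **The plan's own figures.** The plan gives none for the follow-up rows. Its only computed design figure is the chance of seeing at least one adverse event at a true rate of 20%. This reproduces: 1 − 0.8^10 = 89.3% and 1 − 0.8^15 = 96.5%, against the stated > 89% and > 96%. It has no bearing here.

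**Which tables are affected.**

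- Tables 2.1.1 and 2.1.2 are confined by title to Weeks 6 to 12. Neither follow-up nor extension visits can enter them.
- Tables 2.2.4, 2.2.7 and 2.2.8 are continuous and by visit. SAP 5.1 already requires the number of observations, and with no imputation these are observed-case rows with n shown.
- Tables 2.2.1, 2.2.2 and 2.2.6 are categorical and by visit. Here the base is unstated. The same would hold for 2.2.3 and 2.2.5 if they are laid out by visit, which their titles do not say.

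**The contrast of 45 with 0.** The X tables number 2 + 16 + 12 + 4 + 5 + 6 = 45, and none of the 10 efficacy tables is among them. The comparison is not like for like. Two efficacy tables stop at Week 12, and FACIT-F is absent from Protocol Table 2, which leaves 10 − 3 = 7 with possible extension data. On the other side, 5 + 6 = 11 of the 45 are vital-sign and ECG tables, and Table 2 schedules neither. The X suffix does not track what is collected.

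**Timing of Month 1.** Protocol 8.9.1 places it 30 to 35 days (4.3 to 5.0 weeks) after end of treatment. Ignoring visit windows:

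| Last dose | Month 1 visit |
|---|---|
| Week 4 (early stop) | Week 8.3 to 9.0 |
| Week 12 | Week 16.3 to 17.0 |
| First extension visit, Week 20 to 24 | Week 24.3 to 29.0 |

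Month 1 is therefore not a fixed time since Day 1, but it is a fixed time since stopping drug, which is how the protocol defines follow-up.

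**Size, with assumed inputs.** Take N = 25, R responders at Week 12, k responders and m non-responders entering the extension, and no change in anyone's status. The rate among Table 1 attendees is (R − k)/(25 − k − m).

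| R (Week 12 rate) | k | m | Attendees | FAS base |
|---|---|---|---|---|
| 10 (40%) | 5 | 0 | 5/20 = 25% | 5/25 = 20% |
| 10 (40%) | 5 | 3 | 5/17 = 29% | 20% |
| 10 (40%) | 5 | 8 | 5/12 = 42% | 20% |
| 5 (20%) | 2 | 0 | 3/23 = 13% | 3/25 = 12% |
| 5 (20%) | 2 | 10 | 3/13 = 23% | 12% |
| 15 (60%) | 8 | 0 | 7/17 = 41% | 7/25 = 28% |
| 15 (60%) | 8 | 5 | 7/12 = 58% | 28% |

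The attendee rate equals the Week 12 rate when k/(k + m) = R/25, that is, when entrants respond at the same rate as everyone. Entry based on benefit makes a fall the likelier direction. But clinical benefit is not defined as CR or PR, so neither k nor m can be read from the documents. If post-extension follow-up were pooled and all returned unchanged, the first scenario would give 10/25 = 40%.

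**Which reading is natural.** SAP 8.1 and the closing note to the Appendix A table list pair the FAS with the treatment period and the extension population with the extension period. Section 7 does not repeat this, but it is the only convention the SAP states, and it favours keeping post-extension follow-up out of the FAS rows.

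**The case for a change.** The case for a change is a reasonable one. The two follow-up periods share labels, selection into the extension is related to outcome, and the SAP leaves the analyst to choose. As scheduled, the FACIT-F rows at Months 1 to 3 can come only from participants who did not enter the extension. For Table 2.2.6 the selection goes further: footnote k of Protocol Table 1 has hemolysis markers assessed in follow-up when symptoms appear or new treatment starts. Extension hemoglobin appears only in safety displays, without the transfusion condition of SAP 7.2. The original SAP predates the extension, and 5.1 is not named among the sections later updated, so the sentence may have been written for a single follow-up period. A few words would settle it.

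All of this stands as description. It does not show that the plan, followed as written, produces a wrong result.

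- A row restricted to those assessed, with n shown, is an accurate account of those participants. The harm arises only if it is compared with Week 12 as though the same people were in both.
- CR and PR after baseline are tabulated by visit, so extension visits would add rows and could not inflate a cumulative count.
- SAP 9 lists no tables for the interim, so nothing commits the sponsor to follow-up rows there.
- Extension laboratory tests follow site standard of care at the investigator's discretion (Protocol 8.1 and 8.3.5), a plausible reason for planning no by-visit response table.
- Neither Protocol 3 nor SAP 2.2 makes maintenance of response an endpoint. Splitting about 25 participants by period and Week 12 response would leave very small cells.
- Appendix A refers to shells for nonstandard tables, which are not in the public text. Visit rows and bases may be fixed there.

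**Conclusion.** The gap in wording is real but small, and no change to the plan follows. It is limited to the follow-up rows of secondary descriptive tables, with an unstated percentage base in three tables titled by visit. The Week 6 to 12 primary endpoints are unaffected, no hypothesis is tested, and Listings 2.1 and 2.2 hold each participant's hemoglobin and transfusion data. A sensible analyst would label the post-Week-12 and post-extension periods separately, show the number assessed and note who is in the rows. Appendix A allows such shell changes without an SAP amendment.

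The size of any misreading cannot be derived from the documents. In the assumed scenarios above, the attendee rate runs from about 19 points below the Week 12 rate to about 3 points above it; an FAS base would read lower still. The conclusion rests on two assumptions: that the SAP's separation of treatment and extension periods carries over to efficacy, and that the number assessed appears beside each follow-up percentage. An extension-period response table would be a reasonable exploratory extra and is not needed to correct anything. Readers should not take the follow-up rows as evidence for or against durability of response.
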